10.2.6 Overall Survival

Overall survival (months) is defined as (date of death due to any cause - the start date of treatment +1)/30.4375. Subjects with no documented death will be censored at the last date known to be alive (i.e. latest date collected in the eCRF).

Survival rate at every 6 months will be presented with the corresponding 95% CIs will be estimated using the K-M method. A K-M plot for OS will be presented.

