## 5. STUDY DESIGN AND TREATMENT

### 5.1. Study Design

This is a multicentre, basket, two stage, adaptive single arm Phase II study to examine the efficacy of Debio 1347 administered at the recommended Phase II dose of 80 mg in subjects with solid tumors harboring FGFR1-3 gene fusion/rearrangement. The study will include 3 cohorts of subjects comprising biliary tract cancer (Cohort 1), urothelial cancer (Cohort 2) and, in Cohort 3, all other solid tumor histologies not included in Cohorts 1-2, such as non small cell lung cancer (NSCLC), head and neck cancer, thyroid cancer, oral cancer, breast cancer, prostate cancer and others but excluding primary brain tumors.

Stage 1 will require 27 evaluable subjects across the three cohorts assuming an equal accrual rate per cohort. Stage 2 will require 86 evaluable subjects across all cohorts or per individual cohort depending on results of assessments scheduled at the end of Stage 1 (see graphical algorithm below and Section 11). Assuming a drop out rate of 10%, up to 125 subjects will be enrolled into the study.

Subjects will be treated with Debio 1347 daily in 28-day cycles until the occurrence of disease progression (clinical or radiologic) or unacceptable toxicity (other treatment discontinuation criteria are described in Section 8.4.1). Subject safety (AEs) and survival will be followed-up respectively for 30 days after the last Debio 1347 dose and every 12 weeks from treatment end until death or loss to follow-up but no longer than for a total of 2 years after the last subject has discontinued treatment. Disease status will be followed-up every 12 weeks only in subjects without PD from treatment end until PD, death or loss to follow-up but no longer than for a total of 2 years after the last subject has discontinued treatment.

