1 INTRODUCTION

This statistical analysis plan (SAP) describes the statistical analyses planned to be performed for the study Debio 1347-201 entitled “A Phase II basket study of the oral selective pan-FGFR inhibitor Debio 1347 in subjects with solid tumors harboring a fusion of FGFR1, FGFR2 or FGFR3”. The SAP is compliant with the study protocol version 3, dated of July 16th 2020. The SAP will be finalized prior to the database lock for the main analysis.

The rationale for Protocol Amendment 2 (PA2) was

- The results of data monitoring reviews of pooled data (Section **Error! Reference source not found.**) showed that the antitumor activity of Debio 1347 was lower than initially assumed at the time the protocol was developed. Considering that further enrolment is unlikely to substantially change the magnitude of the efficacy observed up to now, Debiopharm decided to permanently halt the enrolment in the study after consultation with the IDMC on June 10th, 2020.

After implementation of PA2:

- After consenting to PA2, on-treatment subjects will no longer be assessed for efficacy in the study, but only for safety.
- Off-treatment subjects will not be followed for disease status or survival in the study, but only for safety up to 30 days post last dose of Debio 1347.
- Subjects will complete study participation at 30 days after the last dose of Debio 1347. In the case of off-treatment subjects with >30 days and <2 years follow-up at the time of PA2 implementation, then these subjects can complete study participation immediately.

The SAP will pre-specify the statistical consideration for the analysis of study data to ensure validity of study findings and conclusions regarding study objectives.

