The interim analysis was not conducted as planned (as detailed in section 10.8.2). Based on an initial statistical review of pooled data, the antitumor activity for Debio 1347 is lower than initially assumed at the time the protocol was developed. Debiopharm decided to permanently halt the enrollment in stage 1 of the study after consultation with the IDMC on June 10th, 2020.

The subsequent protocol amendment 2 (PA2) was implemented to modify the study design in the following ways:

- All ongoing patients (on-treatment subjects and off-treatment subjects still under follow-up) will be re-consented to PA2.
- Subjects showing clinical benefit may remain on-treatment with Debio 1347 until a condition to stop treatment is met.

- After consenting to PA2, on-treatment subjects will no longer be assessed for efficacy in the study, but only for AE, SAE and AESI as described in the pared down study plan of PA2 (**Error! Reference source not found.**).
- Off-treatment subjects will not be followed for disease status or survival in the study, but only for AE, SAE and AESI up to 30 days after the last dose of Debio 1347.
- Subjects will complete study participation at 30 days after the last dose of Debio 1347. In the case of off-treatment subjects with >30 days and <2 years follow-up at the time of PA2 implementation, then these subjects can end (i.e. complete) study participation immediately.
- Subsequent efficacy data collected through standard institutional care practice in on-treatment and off-treatment subjects will not be collected in the eCRF.
- No further IDMC meetings will be required.

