10.2 Efficacy Analyses

The efficacy analysis will be performed on the ITT population as the primary analysis. All efficacy analyses will be repeated on the mITT and PP population as supportive analysis, unless otherwise stated.

PA2 shortens the data collection period for efficacy data. Compared to early enrolled subjects, the later enrolled subjects will systematically have less tumor response assessments at PA2 implementation and time to event variables censored at date of last dose. There will be no additional statistical considerations to specifically address these systematic differences between earlier and later enrolled patients, and therefore, the planned statistical methods remain same as before PA2 was implemented.

Also, since the homogeneity assessment at interim analysis was not conducted, the efficacy endpoints will be analyzed and reported by cohort and pooled total subjects.

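### After Amendment 2, how long OS is followed depends on treatment status; SAP 10.2.6 sets no common cut-off, so OS censoring is informative, probably upward in effect and of uncertain size

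*SAP*

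**What the plan says.** **Before Amendment 2.** Protocol 5.1 planned survival contacts for every off-treatment subject: "every 12 weeks from treatment end until death or loss to follow-up but no longer than for a total of 2 years", counted from when the last subject stops treatment.

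**After Amendment 2, off treatment.** SAP 4.1.2: "Off-treatment subjects will not be followed for disease status or survival in the study, but only for AE, SAE and AESI", and that only up to 30 days after the last dose. For those already more than 30 days past it, SAP 1 adds "then these subjects can complete study participation immediately".

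**After Amendment 2, on treatment.** SAP 4.1.2: "Subjects showing clinical benefit may remain on-treatment with Debio 1347 until a condition to stop treatment is met". Of their data it says "on-treatment subjects will no longer be assessed for efficacy in the study, but only for AE, SAE and AESI". The protocol's rationale for the amendment has them seen at least every 2 months, so dated eCRF entries continue. Once they stop, they too have only the 30-day safety follow-up (Protocol 8.2.7).

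**Censoring.** SAP 10.2.6 censors OS with this rule: "Subjects with no documented death will be censored at the last date known to be alive (i.e. latest date collected in the eCRF". DOR (10.2.2) and PFS (10.2.5) are censored at the last adequate tumor assessment. The introduction to 10.2 nevertheless describes later-enrolled subjects as having "time to event variables censored at date of last dose". It plans no adjustment for the amendment.

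**Timing and output.** SAP 9.3 runs the main analysis after the last end-of-study visit. Protocol 11.5.6.2 asks for OS rates at 1 and 2 years; SAP 10.2.6 asks for them every 6 months.

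**The concern.** Kaplan-Meier assumes that a subject censored at a given time has the same future risk as those who remain at risk. A common calendar cut-off meets this if risk does not depend on entry date. Follow-up that ends at Amendment 2 for subjects off drug, but continues for those still benefiting, does not meet it. Subjects who stay on drug past the amendment are then censored 30 days after the last dose, and progression is one of the main reasons for stopping.

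SAP 10.2 recognises only that later-enrolled subjects have less follow-up. That difference alone would be ordinary administrative censoring. It does not mention the on/off-treatment difference, which is what can bias OS.

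Two wording faults add to this. The latest date in the eCRF need not show that the subject was alive, since an administrative entry would qualify. The last-dose phrase in 10.2 disagrees with all three endpoint-specific rules. At stake is whether the reported OS curve describes the treated population.

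**Working it through.** The documents state no OS rate, median or event count, so there is no figure to reproduce. The check is of direction and plausible size.

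**1. Direction.** At time t, let p be the share of true survivors who are on treatment and p′ the share on treatment in the analysed risk set. Let h_on and h_off be the death hazards.

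- True hazard: p·h_on + (1 − p)·h_off
- Analysed hazard: p′·h_on + (1 − p′)·h_off
- True minus analysed: (p′ − p)(h_off − h_on)

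Post-amendment time comes only from subjects on treatment or within 30 days of it, so p′ exceeds p once such time enters. OS is overstated if h_off > h_on and unbiased if they are equal. A simulated control with equal hazards gave 18.8% against a true 18.9% at 12 months.

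**2. Size, vital status known at the amendment.** From the documents: the 30-day tail, immediate exit for those further off treatment, and continued observation on treatment. Assumed: uniform accrual over 16 months, the amendment 1.5 months later (maximum prior follow-up 16 + 1.5 = 17.5 months), at most 18 months of further observation, exponential times, 400,000 subjects per setting.

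| Median treatment | Monthly hazard on / off | True 12-month OS | SAP rule | Difference |
|---|---|---|---|---|
| 3 months | 0.05 / 0.10 | 37.5% | 38.9% | +1.4 |
| 4 months | 0.02 / 0.12 | 42.5% | 46.7% | +4.2 |
| 6 months | 0.02 / 0.12 | 49.6% | 54.5% | +4.9 |

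- In the 4-month setting, the 17-month rate is 33.1% against 25.5% (+7.6).
- With treatment near the phase I median of 7.3 weeks (Protocol 3.3.2), the 12-month bias is about 1 point, and nearer 0.5 with a smaller hazard contrast.
- Limiting post-amendment observation to 3 months cuts the 4-month setting from about 4 points to about 2.
- A common cut-off at the amendment matched truth within 0.1 point wherever estimable.

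**3. A second model.** Assumed: 20–60% of subjects benefit, with median treatment 7.8 months for them and 1.7 months for the rest; on-treatment hazard 0.01–0.03; post-treatment median survival 3–8 months; amendment 2 months after accrual ends.

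- Accrual 15–18 months: +3.8 to +6.2 points at 12 months. The base case is 44.3% against 39.0%, and 34.2% against 21.7% at 18 months.
- Accrual 9 months: 52.5% against 39.0%, and 58.5% against 44.8%. Here 12 months lies beyond the 9 + 2 = 11 months of pre-amendment follow-up, so a common cut-off cannot estimate that rate.

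**4. Stale contact dates.** Suppose off-treatment survivors are instead censored at their last 12-weekly contact while deaths count up to the amendment. Over five hazard and duration settings with the accrual of step 2, the SAP rule is then off by +2.2, −2.7, +0.8, +0.5 and +3.8 points at 12 months. The negative case uses treatment near 7.3 weeks (28.4% against 31.1%). In these settings, censoring each subject at the earlier of last contact and amendment is 1.9 to 3.9 points too low. Any cut-off therefore needs vital status confirmed at that date.

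**The case against.** **The direction is not proved.** The documents give no hazards, no accrual dates and no count on treatment at the amendment. Step 4 shows that stale contact dates can offset the bias or reverse it at 12 months. This stands, so the upward claim is conditional.

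**The exposed period may be short.** SAP 9.3 says the study ended sooner than expected, and shorter post-amendment observation shrinks the bias. This stands as a limit on size.

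**The protocol may already imply a cut-off.** Protocol 11 applies its statistical plan to the period up to Amendment 2 and captures only safety data afterwards. That reading is fair, but SAP 10.2.6 does not apply it, and a programmer following the SAP would use later dates.

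**The last-dose phrase is not an operative rule.** A reader might infer that SAP 10.2 credits unscanned time on drug as progression-free in PFS and DOR. The documents do not support that: the phrase sits in a description of consequences, and the same paragraph leaves the planned methods unchanged. What remains is a contradiction in wording that should be removed.

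**OS is descriptive and secondary**, in a trial halted for low activity. This stands and limits the importance.

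**Conclusion.** The concern holds in a limited form. The text makes OS follow-up after Amendment 2 depend on treatment status, and 10.2.6 has no cut-off to neutralise it, so the censoring is informative. If the hazard is higher off treatment, OS is overstated by roughly 0.5 to 5 points at 12 months under the assumptions in step 2, and by more later.

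A reader might infer a firm, large upward bias from the double-digit differences that some settings produce. The documents do not support that. Those figures need short accrual or late time points that lie beyond the follow-up available before the amendment, and no input to them is documented. Nor does the whole curve rest on benefiting subjects: time runs from treatment start, so off-treatment subjects enrolled early contribute up to the amendment and the bias until then is partial.

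The change should be made, but this is not a critical defect. The ORR test is unaffected.

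**What to change.** 1. **Common cut-off.** Make the main OS analysis use one calendar date, that of Amendment 2 implementation, and count deaths and follow-up only to that date. Censor subjects confirmed alive at or after it at the cut-off, and the others at their last documented alive date. SAP 4.1.2 has all ongoing subjects re-consented, including those off treatment and still under follow-up, so that contact can supply vital status. Keep the version using all eCRF dates as a labelled sensitivity analysis, and report numbers at risk.
2. **Alive dates.** In 10.2.6, replace the eCRF parenthesis with dates that show the subject alive: visit, dose, scan, sample, survival contact or re-consent contact.
3. **Wording of 10.2.** Delete or correct "time to event variables censored at date of last dose" so that 10.2.2, 10.2.5 and 10.2.6 govern.

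**Cost.** SAP wording and one derivation. On-treatment time and deaths after the amendment leave the main OS analysis. Late rates, possibly 18 months and the protocol's 2-year rate, may not be estimable and should then be reported as such. If many off-treatment survivors have no contact at or after the cut-off, some of the downward error in step 4 remains, so their number should be reported.

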### 8.2.7. Follow-up Assessments

As per Protocol Amendment N° 2, patients who discontinue study treatment will only undergo a safety follow-up (i.e. during 30 days post last Debio 1347 dose administration). Patients will not be followed for disease status and survival follow up. Sub-section “a” below applies exclusively. After treatment discontinuation (= EOT visit), subjects will be followed up for:

- a. Safety** (AEs/SAEs) for 30 days from the date of the last Debio 1347 dose; after this period, the Investigator should report to the Sponsor any unusual safety information or any safety information that appears to be related to the study drug;

- b. **Survival** every 12 weeks ( $\pm$  14 days) from the date of the last Debio 1347 dose until death or loss to follow-up but no longer than for a total of 2 years after the last subject discontinued treatment;
- c. **Disease status** only in subjects without PD every 12 weeks ( $\pm$  14 days) from the date of the last Debio 1347 dose until PD, death or loss to follow-up but no longer than for a total of 2 years after the last subject discontinued treatment;
- d. **Pregnancy screening** every 28 days for 6 months after the last Debio 1347 dose. All pregnancies detected during the 6-month post-EOT follow-up period should be reported according to the standard process described in Section 9.7

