#### 9.1.2. Serious Adverse Event

A SAE is any untoward medical occurrence that at any dose:

- Results in death;
- Is life threatening (i.e., puts the patient at immediate risk of death);
- Requires inpatient hospitalisation or prolongation of existing hospitalisation;

**Of note:** In general, hospitalization signifies that the subject has been detained (at least an overnight stay) at the hospital or emergency ward for observation and/or treatment that would not have been appropriate in the physician's office or out-patient setting. Complications that occur during

hospitalisation are AEs. If a complication prolongs hospitalization or fulfils any other serious criteria, the event is serious.

Hospitalization for elective treatment of a pre-existing condition that did not worsen from baseline is not considered an AE.

- Results in persistent or significant disability/incapacity;

**Of note:** The term disability means a substantial disruption of a person's ability to conduct normal life functions. This definition is not intended to include experiences of relatively minor medical significance such as uncomplicated headache, nausea, vomiting, diarrhea, influenza, and accidental trauma (e.g., strained ankle) which may interfere or prevent everyday life functions but do not constitute a substantial disruption.

- Is a congenital anomaly/birth defect, or
- Is otherwise medically significant: Important medical events that may not immediately be life threatening or result in death or hospitalisation, but that jeopardise the patient/subject or require intervention to prevent one of the outcomes listed in the definitions above shall also be considered as serious.

**Non-serious:** All AEs that do not correspond to the definition of SAE are considered as non-serious.

**Reporting of disease progression:** Disease progression/recurrence, symptoms and signs related to tumour progression/recurrence, e.g., hospitalisation due to a tumour progression, should not be reported as an AE or SAE.

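### After Amendment 2, OS follow-up depends on treatment status, so censoring at the latest eCRF date is dependent censoring and is expected to overstate late OS by an amount the documents cannot fix

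*SAP*

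**What the plan says.** Before Amendment 2, survival was followed after treatment end for every subject, whatever the reason for stopping: "every 12 weeks from treatment end until death or loss to follow-up" (Protocol 5.1).

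Amendment 2 changes this in three ways:
- **Off treatment.** "Off-treatment subjects will not be followed for disease status or survival in the study" (SAP 4.1.2). Protocol 8.2.7 agrees: "Patients will not be followed for disease status and survival follow up". Of those more than 30 days past last dose, the SAP says "then these subjects can end (i.e. complete) study participation immediately".
- **On treatment.** "Subjects showing clinical benefit may remain on-treatment with Debio 1347 until a condition to stop treatment is met" (SAP 4.1.2). The protocol's rationale for the amendment requires safety contact at least every two months. Participation ends 30 days after the last dose.
- **Analysis timing.** SAP 9.3 now runs the main analysis after the last subject's EOS visit, so dates collected after Amendment 2 will be in the database.

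The OS rule in SAP 10.2.6 is: "Subjects with no documented death will be censored at the last date known to be alive (i.e. latest date collected in the eCRF". On the effect of the amendment, SAP 10.2 says: "There will be no additional statistical considerations to specifically address these systematic differences between earlier and later enrolled patients". In the same paragraph it describes the time-to-event variables of later-enrolled subjects as censored on the day of last dose. For OS, that does not agree with 10.2.6.

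**The concern.** Kaplan-Meier estimation needs subjects censored at a given time to have the same outlook as those who stay under observation. Stopping all follow-up on one calendar date would meet that condition, and shorter follow-up in later-enrolled subjects is no problem in itself. SAP 10.2 considers only that second issue.

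The amendment does something else. A subject who has stopped treatment, usually for progression or toxicity, leaves the OS risk set at once or within 30 days. A subject still benefiting stays in, then leaves about a month after treatment fails, just as risk can be expected to rise. Beyond Amendment 2 the curve is carried by the better-prognosis subjects, and their later deaths are mostly out of view. The late survival rates, and any median read from that part of the curve, would be too high. The planned 95% confidence intervals would not reflect this, and a larger sample would not remove it.

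**Working it through.** The documents give no OS assumption (no median, rate or event count), so there is no planned figure to reproduce. The check asks how far the rule moves 12-month OS under stated assumptions.

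**Inputs from the documents**
- Observation ends 30 days after last dose once Amendment 2 applies (SAP 4.1.2); taken as 1 month.
- Median treatment duration in the phase I dose escalation was 7.3 weeks (Protocol 3.3.2): 7.3 × 7 / 30.4375 = 1.7 months.
- The second IDMC review covered 63 evaluable subjects (SAP 10.8.2).

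**Assumptions (not in the documents)**
- Uniform accrual over 14 months, with Amendment 2 two months after the last entry.
- Exponential time to stopping drug, median 1.7 or 4 months.
- Exponential survival after stopping, median 6 months.
- Death hazard on drug equal to the off-drug hazard divided by a ratio of 1, 2, 4 or 8, or equal to zero.

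**True OS.** With stopping hazard a, on-drug death hazard h1 and off-drug death hazard h2:

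S(t) = e^(−(a+h1)t) + [a / (a + h1 − h2)] × [e^(−h2·t) − e^(−(a+h1)t)]

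Example, median 4 months on drug and ratio 4: a = ln2/4 = 0.1733, h2 = ln2/6 = 0.1155, h1 = 0.1155/4 = 0.0289. At 12 months, S = 0.0884 + 2.0 × (0.2500 − 0.0884) = 0.412.

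**Rules compared**, by Kaplan-Meier on 1,000,000 simulated subjects per row:
- SAP rule: deaths count, and others are censored, up to the later of Amendment 2 and last dose + 1 month.
- Common cut-off: everyone stops at Amendment 2.

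12-month OS, %:

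| Median on drug (months) | Hazard ratio off/on | On drug at Amendment 2 | True | Common cut-off | SAP rule | Bias, SAP rule (points) |
|---|---|---|---|---|---|---|
| 1.7 | 2 | 6.0 | 29.1 | 29.1 | 29.6 | +0.5 |
| 1.7 | 4 | 6.8 | 31.5 | 31.5 | 32.4 | +0.9 |
| 1.7 | 8 | 7.2 | 33.0 | 33.1 | 34.2 | +1.2 |
| 4 | 2 | 18.8 | 34.4 | 34.4 | 36.3 | +1.9 |
| 4 | 4 | 22.2 | 41.2 | 41.3 | 45.0 | +3.8 |
| 4 | 8 | 24.2 | 45.3 | 45.2 | 50.2 | +4.9 |
| 4 | no deaths on drug | 26.5 | 50.0 | 50.1 | 56.3 | +6.3 |

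Repeat runs move the biases by a tenth or two, so I read them as about +0.4 to +1.3 points at 1.7 months and about +2 to +5 points at 4 months. At ratio 1 the bias is nil.

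**Where in the curve.** For median 4 months and ratio 4, the bias is 71.1 − 70.3 = +0.8 points at 6 months, 45.0 − 41.2 = +3.8 at 12 months and 36.4 − 30.6 = +5.8 at 15 months. The median moves from 10.0 to 10.6 months.

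**Against sampling error.** With 63 subjects and no censoring, the standard error near 41% is √(0.412 × 0.588 / 63) = 6.2 points. With censoring, repeated samples of 63 gave 7 to 12 points in scenarios with 12 or 18 months of accrual.

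**The case against.** The strongest reply has four parts.

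**The rule is standard and the bias may be negligible.** Censoring at last known alive is normal practice. The only treatment duration in the documents is 7.3 weeks, and central unconfirmed ORR at the second IDMC meeting was 4.8% (SAP Table 6), which gives no reason to expect long treatment. At 1.7 months the bias is about a point, well inside sampling error. This stands as to size. It does not remove the dependence, and the phase I figure comes from a mixed population over a range of doses.

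**The larger figures need nobody to die on drug.** This also stands. A reader might take about +6 points as the likely effect, but that requires zero on-treatment mortality. In phase I, 7 of 58 subjects (12.1%) had a Grade 5 treatment-emergent event (Protocol 3.3.2).

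**Deaths are not shown to be lost.** A reader might infer that progression deaths after Amendment 2 go unrecorded: SAP 10.3 limits eCRF entry to AEs, SAEs and AESIs, and the protocol says of progression and its signs, for example, "hospitalisation due to a tumour progression, should not be reported as an AE or SAE". The documents do not support that. The same section makes death a seriousness criterion, and Protocol 11.5.7 and SAP 10.3.2 list all deaths with reasons. At most, the eCRF route for a progression death is unclear. I therefore give no figure for missed deaths.

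**The censoring rule is itself unsettled.** If the last-dose wording in SAP 10.2 governed OS, the calculation above would not apply as it stands. But that reading also ties censoring to stopping treatment, so it offers no safe alternative.

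**Conclusion.** The point holds in a limited form. After Amendment 2 the OS censoring time depends on treatment status, and SAP 10.2 declines to address it. The upward direction needs higher mortality off drug than on it. The documents support that qualitatively, since treatment ends mainly at progression or toxicity and those who remain are described as benefiting, but they give no hazards. So OS is expected to be overstated, mainly in the late part of the curve.

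Under the stated assumptions the 12-month bias runs from about +0.4 to +1.3 points (1.7 months on drug) to about +2 to +5 points (4 months), that is, from negligible to somewhat less than one standard error with 63 subjects. The number on treatment at Amendment 2 drives the size and is not reported.

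A reader might infer that the trial's efficacy conclusion is affected. It is not: OS is secondary, descriptive and untested, and ORR does not use this rule.

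**What to change.** In SAP 10.2.6:
- Name one calendar cut-off date for OS, no later than the start of Amendment 2 implementation, and apply it to all subjects whatever their treatment status. The documents give no single implementation date, and the change for on-treatment subjects follows individual consent, so an actual date is needed. The protocol version 3 date, 16 July 2020 (SAP 1), would serve.
- Count deaths up to that date. Censor everyone else at the earlier of last date known alive and that date.
- Report the number on treatment at the cut-off.
- Show OS using all eCRF dates as a labelled sensitivity analysis.
- Reconcile the last-dose statement in SAP 10.2 with 10.2.6, and state how a progression death after Amendment 2 reaches the eCRF.

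The work is a few sentences and one derivation. The real cost is a shorter curve. Under the assumptions above, follow-up could not exceed 14 + 2 = 16 months, so an 18-month rate, or the 2-year rate in Protocol 11.5.6.2, might not be estimable.

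Alive status at the cut-off may also be out of date for off-treatment subjects. Survival contacts were 12-weekly (± 14 days). SAP 4.1.2 speaks of re-consenting all ongoing subjects, but the post-amendment study plan (SAP Table 11) marks that consent only under ongoing treatment. Re-consent should not be relied on to establish survival status.
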